7.2.2 Primary endpoint analyses

The difference in percent change from baseline in total abscess and inflammatory nodule at Week 12 between spesolimab and placebo is the primary endpoint of this trial. All on-treatment data are planned to be included into analysis but any data after use of any rescue therapy will be censored in line with the primary objective to estimate the treatment effect in treated patients assuming they do not receive rescue therapy (primary estimand). To account for the repeated nature of the data, the primary analysis is a restricted maximum likelihood (REML) based approach using a mixed model with repeated measurements (MMRM) comparing the adjusted relevant difference between the two arms.

The analysis will include the fixed categorical effects of treatment at each visit, stratum and the fixed continuous effect of baseline at each visit. Visit will be treated as the repeated measure with an unstructured covariance structure to model the within-patient measurements.

The statistical model will be as follows:

$$y_{ijkm} = \beta_j S_i + \tau_{jk} + \Phi_m + e_{ij}$$

With

- y_{ijkm} response variable for patient i in stratum m at visit j receiving treatment k
- S_i baseline measurement of patient i , $i=1,2,\dots$
- β_j coefficient of baseline effect at visit j
- τ_{jk} effect of treatment k at visit j , $j=3,\dots,9$ and $k=1, 2$
- Φ_m effect of stratum m , $m=1,2$
- e_{ij} random error associated with visit j of patient i .

Errors are independent between patients with $e_{ij} \sim N_z(0, \Sigma)$ and Σ is an unstructured covariance matrix.

The Kenward-Roger approximation will be used to estimate denominator degrees of freedom and adjust standard errors. Due to the exploratory character of this trial no significance test will be done. However, least-squares means (adjusted means) of each arm as well as adjusted treatment differences will be provided together with two-sided 95 %-confidence intervals for each time point.

The patients will be analysed according to the stratum to which they belong (regardless of any mis-assignment to treatment based on identification of the wrong stratum), as such an error occurs before randomization and is therefore consistent with regulatory guidance. Procedures to follow if the analysis fails to converge will be described in the TSAP.

Secondary analysis of the primary endpoint will include:

[figure not shown]
- A sensitivity analysis utilizing the PPS to evaluate the impact on treatment outcomes of patients who may have relevant deviations from the conduct described in the CTP;
- The effect of stratum (TNFi-naive population versus TNFi-failure population) on the primary endpoint will be descriptively displayed via subgroup assessments.

7.2.3 Secondary endpoint analyses

The continuous secondary endpoints at Week 12 will be analysed using a MMRM approach based upon the estimand concept and model specification as described for the primary endpoint.

The binary secondary endpoints will be evaluated descriptively by treatment arm via frequency tables (with 95% confidence interval) based on TS. If needed, a logistic regression model on binary endpoint at Week 12 will be applied as well. The model will include treatment and stratification factor (TNFi-naive population versus TNFi-failure population) as two categorical variables. As in the case of the primary estimand, any binary data collected after use of any rescue therapy will be censored and then imputed using the NRI method as described in [section 7.3](#).

Further details will be provided in the TSAP.

7.2.5 Safety analyses

Adverse events will be coded using the current version of Medical Dictionary for Regulatory Activities (MedDRA) coding dictionary. Standard Boehringer Ingelheim's summary tables and listings will be produced.

All randomized and treated patients will be included in the safety analysis. In general, safety analyses will be descriptive in nature and will be based on BI standards. No hypothesis testing is planned. Statistical analysis and reporting of adverse events will concentrate on treatment-emergent adverse events (TEAE). To this end, all adverse events occurring between start of treatment and end of the residual effect period will be considered 'treatment-emergent'; the residual effect period (REP) is defined as 16 weeks after the last dose of trial medication. Adverse events that start before first drug intake and deteriorate under treatment will also be considered as 'treatment-emergent'.

Frequency, severity, and causal relationship of adverse events will be tabulated by system organ class (SOC) and preferred term after coding according to the current version of the MedDRA at database lock.

Laboratory data will be analysed both quantitatively as well as qualitatively. The later will be done via comparison of laboratory data to their reference ranges. Values outside the reference range as well as values defined as clinically relevant will be highlighted in the listings. Treatment groups will be compared descriptively with regard to distribution parameters as well as with regard to frequency and percentage of patients with abnormal values or clinically relevant abnormal values. Vital signs, physical examinations, or other safety-relevant data observed at screening, baseline, during the course of the trial and at the end-of-trial evaluation will be assessed with regard to possible changes compared to findings before start of treatment.

Immunogenicity data will be analysed in a descriptive way.

7.2.6 Other Analyses

Biomarker analyses

The statistical analysis for biomarker assessments (cf. [Section 5.4](#)) is mainly descriptive. Summary statistics and summary plots are produced for each assessment at each time point, and for changes from baseline when appropriate.

Correlations between biomarkers and clinical endpoints may also be examined descriptively.

For a visual assessment of this analysis scatter plots may be produced.

Changes in the gene expression profile from baseline to post-baseline will be summarized and described for selected genes. Significantly up- or down-regulated genes are reported.

Thresholds for defining significantly up- and down-regulations will be given in the statistical analysis plan.

Further details will be discussed in the statistical analysis plan.

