5.4.1 Biochemical and cellular biomarkers

The role of spesolimab on the IL36R pathway will be demonstrated by assessing biomarkers in skin biopsies and blood including, but not limited to IL36 α and IL36 γ at different time points post treatment compared to baseline. To demonstrate treatment effect of spesolimab in the peripheral compartment, pre- and at various time points post treatment, physiological response biomarkers including, but not limited to CRP, lipocalin 2, and S100 proteins will be evaluated. In addition, to understand the tissue-specific impact of spesolimab over time, skin biopsies (lesional and non-lesional) will be collected at baseline and at selected time points post treatment. The skin biopsies will be used for assessment of skin protein biomarkers using techniques such as immunohistochemistry (IHC).

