7.5 DETERMINATION OF SAMPLE SIZE

This is a proof of clinical concept trial to explore a benefit of spesolimab over placebo in terms of the primary endpoint, percent change from baseline in total abscess and inflammatory nodule count at Week 12 based on the MMRM method.

With reference to the pivotal trials of Adalimumab [R20-3157] which is the only approved biologic for HS, it is expected that patients on placebo arm could achieve approximately a 20% reduction after 12 weeks of treatment. In contrast, it is expected patients on spesolimab arm could achieve a 60% to 65% reduction which is around 40% to 45% superior to placebo. The standardized deviation is assumed to be 45% for each arm.

The pivotal trials of Adalimumab [R20-3157] shows that the primary endpoint, percent change from baseline in total abscess and inflammatory nodule count at Week 12, is skewed in both active treatment arm and the placebo arm. Under such situation of skewness, for primary endpoint, MMRM method is still valid as the asymptotic normality of the distribution of the point estimate still holds. However, the commonly used “exact” methods for calculating sample size become inappropriate in this case, as they are based on a normality assumption of the data. Therefore, a simulation method is used to calculate the sample size as below:

Step 1: Data for the primary endpoint for both arms are generated from Gamma distributions respectively to allow for skewed distributions. The distributions for the percent change are parameterized using the published summary statistics from Adalimumab trial data [R20-3157]. The 10,000 datasets are generated

Step 2: For each repetition of the 10,000 iterations, the mean difference between the two arms is calculated. The proportion of iterations with a difference of at least 30% in favor of Spesolimab is calculated for each parameterization setting.

It is assumed that there is no missing data for the primary endpoint so the final primary endpoint analysis using MMRM is expected to be on complete data. Therefore, in the sample size calculation, the mean difference between two arms derived from the simulation above,

which only considers the single time point of interest (at week 12) should approximate the week 12 estimate derived from the MMRM method using all time points over time. All calculations are performed on R version 3.3.2 and the results are summarized in [Table 7.5:1](#).

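### The visible text compares spesolimab's pathway and gene-expression effects with baseline only; name the placebo arm as comparator before unblinding

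*Protocol*

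**What the plan says.** Protocol 5.4.1 (Biochemical and cellular biomarkers) states an aim about the drug: "The role of spesolimab on the IL36R pathway will be demonstrated by assessing biomarkers in skin biopsies and blood", assessed "at different time points post treatment compared to baseline". It then gives a second aim for blood markers such as CRP: "To demonstrate treatment effect of spesolimab in the peripheral compartment, pre- and at various time points post treatment". Placebo is not mentioned in that section.

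Protocol 7.2.6 says that the biomarker analysis "is mainly descriptive. Summary statistics and summary plots are produced for each assessment at each time point, and for changes from baseline when appropriate". For RNA it says "Changes in the gene expression profile from baseline to post-baseline will be summarized and described for selected genes", followed at once by "Significantly up- or down-regulated genes are reported". The cut-off is deferred: "Thresholds for defining significantly up- and down-regulations will be given in the statistical analysis plan". No test, arm or contrast is given.

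The SAP does not fill the gap in the text supplied. Section 3 sends biomarker and gene-expression analyses to a separate biomarker SAP, and section 6.6.5 sends the handling of RNA expression to a separate document. Section 7.11.1 names only HS-CRP for the trial report, allows log transformation, and leaves markers reported elsewhere to another document.

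Elsewhere the comparison is explicit. Protocol 7.2.2 and 7.2.3 estimate an adjusted spesolimab-versus-placebo difference for the primary and continuous secondary endpoints, and 7.2.5 says that laboratory data will be compared descriptively between treatment groups.

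**The concern.** A change from baseline answers whether a marker moved over time. Whether spesolimab moved it is a different question, and in a randomized trial the concurrent placebo arm answers it. The protocol expects movement without drug: "it is expected that patients on placebo arm could achieve approximately a 20% reduction after 12 weeks of treatment" (section 7.5). A marker that follows disease activity could fall in both arms for the same reason.

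The words used for the aim and the result (demonstrating a role, demonstrating a treatment effect, significant regulation) are inferential, and the comparator beside them is baseline. A biomarker SAP that followed these sections literally could label a gene significantly regulated, and a reader would credit the drug, when the placebo patients had changed just as much. At stake is the interpretation of the mechanism results. The clinical comparison is not affected.

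**Working it through.** **Inputs from the documents.** Planned arms: 30 spesolimab, 15 placebo (Synopsis). Expected placebo change in abscess and inflammatory nodule count: 20% reduction; SD 45% per arm; planned spesolimab reduction 62% (section 7.5 and Table 7.5:1). The Flowchart applies one schedule to all patients: lesional biopsies at baseline, Week 4 and Week 12; serum markers and whole-blood RNA at baseline and Weeks 4, 8 and 12.

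**The plan's own figure.** No figure is given for biomarkers. The sizing figure from which the 20% and 45% are borrowed does reproduce. SE = 45 × √(1/30 + 1/15) = 14.23, so P(observed difference ≥ 30) = Φ((42 − 30)/14.23) = Φ(0.843) = 80.0%. The protocol states 80.1%.

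**Assumptions that are not in the documents.** The marker's change is normal with SD 1. The same shift d occurs in both arms, so the true drug effect is zero. Tests are two-sided at a nominal 5%. The largest shift, d = 0.44, is the placebo assumption in SD units (20/45 = 0.444). That a gene or protein shifts as far as the lesion count is pure assumption, so smaller values are shown as well.

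**Within-arm test against baseline.** With n = 30, the one-sample t statistic is noncentral t with 29 degrees of freedom and noncentrality d√30; the critical value is 2.045.

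| Shift d (SD) | d√30 | Positive within spesolimab |
|---|---|---|
| 0 | 0 | 5% |
| 0.10 | 0.55 | 8% |
| 0.22 | 1.20 | 21% |
| 0.33 | 1.81 | 42% |
| 0.44 | 2.41 | 64% |

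At the unrounded 20/45 the last entry is 65%. With 20 or 25 evaluable patients at 0.44 SD it is 46% or 56%.

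**Between-arm test.** The common shift cancels in the spesolimab-minus-placebo difference, so the rate stays at the nominal level. Simulation with 30 versus 15 patients gave 4.6% to 5.2% over shifts of 0 to 0.44 SD.

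**Would a stricter cut-off cure it?** At p < 0.001 and 0.44 SD the within-arm test is positive about 14% of the time, against about 0.1% between arms. The rate is lower, but the contrast still answers the wrong question.

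**Would separate displays by arm cure it?** Not if significance in one arm only were read as a drug effect. At 0.44 SD the placebo arm (n = 15) is significant 35.5% of the time, so significance on spesolimab alone occurs in 0.644 × (1 − 0.355) = 42% of cases with no drug effect. The documents do not propose that rule; it is a way in which arm-wise results could be misread.

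**Is the between-arm contrast usable?** For a true difference of 0.93 SD (42/45, the planned clinical effect in SD units) its power is about 82%.

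**The case against.** The strongest reply is that change from baseline is this protocol's usual outcome variable and does not define a test. The primary endpoint is worded the same way and is still compared between arms. Section 7.2.6 says that gene changes are summarized and described, and specifies no test. The tie between significance and change from baseline rests on two adjacent sentences. The document that would settle the matter was not supplied. All of this stands, and it limits the point to what the visible text names and omits.

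Four stronger inferences are tempting, and the documents do not support them.

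- *The plan ignores the placebo samples, or has a 64% false-positive rate.* No test, alpha, marker shift or marker SD appears in the text supplied. The percentages illustrate a type of comparison and are not properties of this plan.
- *Every reported gene will be presented as regulated by spesolimab.* Section 5.4.2 gives the RNA work two aims: genes involved in the drug's mechanism, or in the pathology of the disease. Change over time is relevant to the second.
- *Baseline biopsies are aimed at inflamed sites, so later ones must look better.* Section 5.4.3 does not limit ultrasound targeting to baseline, and the Flowchart schedules ultrasound at all three lesional biopsy visits. The asymmetry is not shown.
- *The proof of concept is undermined.* It rests on the lesion count, which is compared with placebo. Section 5.4 calls these biomarkers exploratory, section 7.1 rules out confirmatory testing, and no decision rule uses a gene call.

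The reply does not remove the gap. Section 5.4.1 states an aim about the drug and names baseline alone. Section 7.2.6 defers the thresholds and further details but never says that the comparison will be with placebo.

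**Conclusion.** The point holds in a limited form. In Protocol 5.4.1 and 7.2.6 baseline is the only comparator named for showing an effect of spesolimab and for the changes described next to the significance label. A drug-effect call made that way would confound drug effect with change that placebo patients may share.

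The size can only be illustrated: about 8% to 64% positive calls per marker with no drug effect, against about 5% for the between-arm test. This assumes shifts of 0.10 to 0.44 SD common to both arms, 30 evaluable spesolimab patients and a nominal two-sided 5%. The unseen biomarker SAP may already use a placebo contrast, in which case only the protocol wording needs aligning. The analysis is exploratory and the primary endpoint is unaffected, so this is a cheap improvement of low severity.

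**What to change.** In Protocol 5.4.1, replace the comparison with baseline by: change from baseline compared with placebo. Name the same contrast for the peripheral markers.

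In 7.2.6, and in the biomarker SAP before unblinding, state that any claim that spesolimab significantly regulates a gene or marker rests on the spesolimab-minus-placebo difference in change from baseline. Set the threshold and the multiplicity control there. Report within-arm changes, including those that serve the disease-pathology aim, descriptively and without attributing them to the drug.

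The cost is wording only, because placebo patients are already sampled at the same visits. The downside is precision: the SE per SD is √(1/30 + 1/15) = 0.316 for the difference, against 1/√30 = 0.183 within the spesolimab arm, about 1.7 times as large. Fewer genes will be called, because the contrast carries the variance of 15 placebo patients.

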7.2.7 Interim Analyses

No interim analysis is planned in this trial.

In order to ensure the patient's safety during the trial, a fully external DMC, independent of the trial and project teams, will review all available unblinded safety data as well as selected efficacy data at regular intervals following first-patient-in. A DMC SAP which describes the analyses required for assessment by the DMC will be produced. Further details will be provided in a DMC charter.

7.3 HANDLING OF MISSING DATA

For primary efficacy endpoint and other endpoints which are continuous in nature, the use of a restricted maximum likelihood (REML)-based mixed model repeated measures (MMRM) approach, if feasible, will ensure that missing data are handled implicitly, via a missing at random assumption, by the statistical model.

For efficacy endpoints which are binary nature, a Non Response Imputation (NRI) approach will be applied to the missing visits up to Week 12; that is, imputing as a failure to achieve a response in the visits with missing endpoint score, however:

- If there are available data at the visits both before and after the visit with a missing outcome, then impute as a success only if both the preceding and the following measurement indicate success and no rescue medication has been given during this period.
- Otherwise, impute as a failure to achieve a response (i.e. no response imputation)

NRI is a conservative imputation scheme because it assumes that use of rescue therapy or missing data due to any other reason is related to treatment failure. In addition, for secondary binary endpoint, HiSCR at Week 12, multiple imputation based method will be applied as sensitivity analysis.

Further sensitivity analyses to assess the robustness of the results on efficacy endpoint will be described in the TSAP if necessary.

With respect to safety evaluations, it is not planned to impute missing values.

7.4 RANDOMIZATION

BI will arrange for the randomization and the packaging and labelling of trial medication. The randomization list will be generated using a validated system, which involves a pseudorandom number generator so that the resulting treatment will be both reproducible and

nonpredictable. The block size will be documented in the Clinical Trial Report. Access to the codes will be controlled and documented.

Stratification of the randomization will be performed for TNFi-naive population versus TNFi-failure population. Approximately 33 patients from TNFi-naive population and 12 patients from TNFi-failure population are planned to be randomized. Once either subpopulation has recruited the planned number of patients, the screening of that subpopulation may be considered to be closed.

Within each stratum, patients will be randomized in a 2:1 randomization ratio to receive Sepsolimab vs placebo. The randomization will be done in blocks to achieve balanced allocation.

The process of randomization is done via an IRT.

7.5 DETERMINATION OF SAMPLE SIZE

This is a proof of clinical concept trial to explore a benefit of spesolimab over placebo in terms of the primary endpoint, percent change from baseline in total abscess and inflammatory nodule count at Week 12 based on the MMRM method.

With reference to the pivotal trials of Adalimumab [R20-3157] which is the only approved biologic for HS, it is expected that patients on placebo arm could achieve approximately a 20% reduction after 12 weeks of treatment. In contrast, it is expected patients on spesolimab arm could achieve a 60% to 65% reduction which is around 40% to 45% superior to placebo. The standardized deviation is assumed to be 45% for each arm.

The pivotal trials of Adalimumab [R20-3157] shows that the primary endpoint, percent change from baseline in total abscess and inflammatory nodule count at Week 12, is skewed in both active treatment arm and the placebo arm. Under such situation of skewness, for primary endpoint, MMRM method is still valid as the asymptotic normality of the distribution of the point estimate still holds. However, the commonly used “exact” methods for calculating sample size become inappropriate in this case, as they are based on a normality assumption of the data. Therefore, a simulation method is used to calculate the sample size as below:

Step 1: Data for the primary endpoint for both arms are generated from Gamma distributions respectively to allow for skewed distributions. The distributions for the percent change are parameterized using the published summary statistics from Adalimumab trial data [R20-3157]. The 10,000 datasets are generated

Step 2: For each repetition of the 10,000 iterations, the mean difference between the two arms is calculated. The proportion of iterations with a difference of at least 30% in favor of Spesolimab is calculated for each parameterization setting.

It is assumed that there is no missing data for the primary endpoint so the final primary endpoint analysis using MMRM is expected to be on complete data. Therefore, in the sample size calculation, the mean difference between two arms derived from the simulation above,

which only considers the single time point of interest (at week 12) should approximate the week 12 estimate derived from the MMRM method using all time points over time. All calculations are performed on R version 3.3.2 and the results are summarized in [Table 7.5:1](#).

Table 7.5: 1 Probabilities to observe at least 30% difference on % change from baseline in total abscess and inflammatory nodule count at Week 12 for spesolimab (30 pts) vs. placebo (15 pts)

Assumed % change from baseline for spesolimab (SD) vs. Placebo (SD)	Probabilities to detect at least 30% difference for spesolimab vs. placebo
-20% (45%) vs -50% (45%)	0 %
-20% (45%) vs -20% (45%)	2.3%
-50% (45%) vs -20% (45%)	49.9%
-55% (45%) vs -20% (45%)	62.9%
-60% (45%) vs -20% (45%)	75.4%
-62% (45%) vs -20% (45%)	80.1%
-65% (45%) vs -20% (45%)	85.2%
-50% (45%) vs -30% (45%)	23.8%
-55% (45%) vs -30% (45%)	35%
-60% (45%) vs -30% (45%)	49.3%
-65% (45%) vs -30% (45%)	62.4%

Therefore, with an expected 62% reduction from baseline in total abscess and inflammatory nodule count at Week 12 on spesolimab and 20% reduction on placebo, the probabilities to detect at least 30% difference of spesolimab relative to placebo is 80.1%.

8. INFORMED CONSENT, TRIAL RECORDS, DATA PROTECTION, PUBLICATION POLICY, AND ADMINISTRATIVE STRUCTURE

The trial will be carried out in compliance with the protocol, the ethical principles laid down in the Declaration of Helsinki, in accordance with the ICH Harmonized Guideline for Good Clinical Practice (GCP), relevant BI Standard Operating Procedures (SOPs), the EU directive 2001/20/EC / EU regulation 536/2014 and other relevant regulations. Investigators and site staff must adhere to these principles. Deviation from the protocol, the principles of ICH GCP or applicable regulations as will be treated as “protocol deviation”.

Standard medical care (prophylactic, diagnostic and therapeutic procedures) remains the responsibility of the treating physician of the patient.

The investigator will inform the sponsor immediately of any urgent safety measures taken to protect the trial patients against any immediate hazard, as well as of any serious breaches of the protocol or of ICH GCP.

The Boehringer Ingelheim transparency and publication policy can be found on the following web page: trials.boehringer-ingelheim.com. The rights of the investigator and of the sponsor with regard to publication of the results of this trial are described in the investigator contract. As a rule, no trial results should be published prior to finalisation of the Clinical Trial Report.

The certificate of insurance cover is made available to the investigator and the patients, and is stored in the ISF.

